4.10.1.3 Handling of Dropouts or Missing Data

Distinct missing data patterns of PIH Overall Disease Severity scores, total lesion counts, inflammatory lesion counts, non-inflammatory lesion counts and Investigator Global Assessment (IGA) scores with their corresponding number and percentage of subjects will be presented in order to establish whether they are monotone or non-monotone.

CCI

GALDERMA R&D RD.06.SPR.204245

The primary method of imputation for missing data of primary and secondary efficacy endpoints will be Multiple Imputation (MI) under the Missing At Random (MAR) assumption.

For the primary MAR based multiple imputation, the MI procedure of the SAS system will be used to generate sets of data with missing values imputed from observed data. It is expected that the pattern of missing data will be monotonic, with slight deviations being corrected by the Markov Chain Monte Carlo (MCMC) method of the MI procedure.

The following steps will be followed:

1. For PIH Overall Disease Severity scores, CCI

. If the pattern is not monotone, the MCMC method of SAS PROC MI will be used to make it monotone. The single chain method will be used, with 200 burn-in iterations and 100 iterations between imputations. In case of lack of convergence with the single chain method, the multiple chain method will be used. Separate imputations by treatment group will be carried out. The minimum values for imputed variables will be set to 0, in order to force PROC MI to redraw another value for imputation when an intended imputed value is less than the 0. For PIH Overall Disease Severity scores only, the maximum value for imputed variables will be set to 8, in order to force PROC MI to redraw another value for imputation when an intended imputed value is greater than the 8.

Imputed values will be rounded to the nearest integer. The seed number will be set to 204245 and fifty (50) imputations will be created.

- 2. SAS PROC MI will be used for imputing missing values of data with monotone missing pattern. If the MCMC method of step 1 was previously employed, one imputation will be made using each of the fifty (50) MCMC-imputed datasets. If the MCMC method of step 1 was not previously employed, fifty (50) imputations will be created assuming the data are Missing At Random. The seed number will be set to 204245. These imputations will use the following models:
 - 2.1. For total, inflammatory and non-inflammatory lesion counts, a predictive mean matching method will be used with covariates for non-missing total, inflammatory and non-inflammatory lesion count from earlier scheduled time points including baseline. The number of closest observations to be used in the selection of the imputed values will be set to 5. Separate imputations by treatment group will be carried out. The minimum values for imputed variables will be set to 0, in order to force PROC MI to redraw another value for imputation when an intended imputed value is less than the 0. Imputed values will be rounded to the nearest integer. Absolute and percent change from baseline in total, inflammatory and non-inflammatory lesion counts will be derived from the corresponding imputed lesion counts.
 - 2.2. For ordinal PIH Overall Disease Severity scores and CCL and a logistic regression model based on fully conditional specification method with 200 burn-in iterations will be used with covariates for non-missing ordinal PIH Overall Disease Severity scores or CCL from earlier scheduled time points including baseline. Separate imputations by treatment group will be carried out. CCL
- 3. The imputed datasets will be analyzed as specified in sections 4.10.2.
- 4. The resulting analysis on the imputed datasets will then be combined to produce a single set of statistics as follows:

- 4.1. For PIH Overall Disease Severity scores, CC , results from the ANCOVA analysis will be combined using the SAS PROC MIANALYZE.
- 4.2. For binary outcome, the results from the Cochran-Mantel-Haenszel (CMH) analysis will be combined using the Wilson-Hilferty transformation to produce a pooled CMH statistic and p-value. The differences in proportions and standard errors will be combined using the SAS PROC MIANALYZE. The resulting pooled difference and standard error will be used to produce the confidence interval based on the large-sample approximation method for binary data without using continuity correction. These methods will be used as described in the Bohdana Ratitch, et al. [Bohdana Ratitch, et al., 2013].

The number of fifty (50) imputations was selected in order to prevent a power falloff due to choosing a number of imputations too small.

To assess the robustness of the primary efficacy results, sensitivity analyses of the primary endpoint will be conducted as follows:

- 1. Missing data of primary endpoint will be imputed using a Pattern-Mixture Model (PMM) for implementing a Copy Reference (CR) under the Missing Not At Random (MNAR) assumption, by using the profiles from Vehicle subjects with observed data to impute missing data. The process will be the same described for the MAR analysis, only the assumption about missing mechanism will be changed.
- 2. Missing data of primary endpoint will be imputed using Last Observation Carried Forward (LOCF).
- 3. Observed Case (OC) analysis.
- 4. Per Protocol (PP) analysis.

4.10.1.4 Multiple Comparisons/Multiplicity

In order to maintain the overall type I error rate at 0.05, a predefined hierarchal testing procedure will be implemented to test the Trifarotene 50 μ g/g cream treatment against vehicle cream treatment on primary endpoint and PIH related secondary endpoints.

The hypothesis test for the primary endpoint will be evaluated on the ITT population at the significance level $\alpha = 0.05$.

The hypothesis tests for the PIH related secondary endpoints are conditional on the success of the primary endpoint.

The hypothesis tests for the secondary efficacy endpoints will be evaluated on the ITT population according to the following predefined order, all at the same significance level $\alpha = 0.05$, moving to the next hypothesis test only after a success on the previous hypothesis test.

- 1) Percent change from Baseline in PIH Overall Disease Severity scores at Week 24
- 2) Absolute change from Baseline in PIH Overall Disease Severity scores at Week 20
- 3) Percent change from Baseline in PIH Overall Disease Severity scores at Week 20
- 4) Absolute change from Baseline in PIH Overall Disease Severity scores at Week 16
- 5) Percent change from Baseline in PIH Overall Disease Severity scores at Week 16

01-Jun-2023 00:00:00

Approved

6) Absolute change from Baseline in PIH Overall Disease Severity scores at Week 12

7) Percent change from Baseline in PIH Overall Disease Severity scores at Week 12

This approach does not inflate the Type I error rate as long as the hypothesis tests for the secondary efficacy endpoints are conditional on the success of the primary, there is a prospective specification of the testing sequence and no further testing is performed once the sequence breaks, that is, further testing stops as soon as there is a failure of a hypothesis test in the sequence to show significance at the predefined alpha level.

No hypothesis test will be evaluated for the other efficacy endpoints. p-values and 95% confidence intervals will be presented for descriptive purposes only.

4.10.1.5 Interim Analyses

Not Applicable.

4.10.1.6 Examination of Subgroups

There is no planned subgroup analysis.

4.10.2 Primary Efficacy Variable – Absolute change from Baseline in PIH Overall Disease Severity scores at week 24

4.10.2.1 Primary Efficacy Analysis

The analysis of Primary efficacy endpoint will be based upon ITT population.

The primary variable for the assessment of efficacy is the Absolute change from Baseline in PIH Overall Disease Severity scores of the face assessed by the investigator at Week 24 (or ET).

Overall Disease Severity Hyperpigmentation Score is graded from 0 to 8 as follows:

- Grade 0 Normal
- Grade 1 Present, but <mild
- Grade 2 Mild (slightly noticeable)
- Grade 3 Between mild and moderate
- Grade 4 Moderate
- Grade 5 Between moderate and marked
- Grade 6 Marked (distinctive)
- Grade 7 Between marked and severe
- Grade 8 Severe (very distinctive)

Missing data will be imputed as per primary method of imputation for missing data described in section Handling of Dropouts or Missing Data

The effect of treatment in terms of the absolute change from Baseline to Week 24 in PIH Overall Disease Severity scores of the face will be analyzed using analysis of covariance (ANCOVA). The statistical model will assess the main effect of treatment, adjusted for center and baseline score as fixed effects. The treatment effect will be estimated using the difference between the treatments least squares means (adjusted means). The 95% confidence interval for the difference between the treatments least squares means and the p-value from the hypothesis test of no difference between the treatment groups will be presented.

4.10.2.2 Primary Efficacy Sensitivity Analyses

Four sensitivity analyses will be conducted to assess the robustness of the primary efficacy results.

Imputation using a PMM

Missing data of primary endpoint will be imputed using a PMM for implementing a CR under the MNAR assumption, by using the profiles from Vehicle subjects with observed data to impute missing data. The analysis will be based upon the ITT population.

Last Observation Carried Forward (LOCF) analysis.

Missing post-Baseline data of primary endpoint will be carried forward from the last non-missing post-Baseline value. The analysis will be based upon the ITT population.

Observed Case (OC) analysis

The ANCOVA analysis will be performed on data without any imputation. The analysis will be based upon the ITT population.

Per Protocol (PP) analysis

Missing data will be imputed using the same imputation method as for the primary analyses (MI under the MAR assumption). The analysis will be based upon the PP population.

By-subject listings of the primary efficacy data will be provided.

4.10.3 Secondary Efficacy Variables

All secondary efficacy endpoint analyses will be based upon ITT population.

Percent change from Baseline in PIH Overall Disease Severity scores at week 24

Missing data will be imputed as per primary method of imputation for missing data described in section Handling of Dropouts or Missing Data

The same analysis as described for primary efficacy variable will be repeated for percent change from Baseline to Week 24.

Absolute and percent change from Baseline in PIH Overall Disease Severity scores will be analyzed at Week 12, 16 and 20

Absolute and percent change from Baseline in PIH Overall Disease Severity scores at Week 12, 16 and 20 will be calculated as for Week 24.

Missing data will be imputed as per primary method of imputation for missing data described in section Handling of Dropouts or Missing Data

The same analysis as described for primary efficacy variable will be repeated for:

- Absolute change from Baseline to Week 20
- Percent change from Baseline to Week 20
- Absolute change from Baseline to Week 16

- Percent change from Baseline to Week 16
- Absolute change from Baseline to Week 12
- Percent change from Baseline to Week 12

PIH Overall Disease Severity scores

PIH Overall Disease Severity scores assessed by the investigator will be summarized descriptively by treatment group based upon the ITT population in terms of absolute values at Baseline, Week 12, 16, 20 and 24, absolute changes and percent changes from baseline at Week 12, 16, 20 and 24.

Proportions of subjects across PIH Overall Disease Severity scores at Baseline, Week 12, 16, 20 and 24 will also be summarized by treatment group using tables of frequency.

CCI Effective Date: 26 Nov 19

CCL

1.0

CD5789.SPR204245.SAP.V01 - Final Version 03F

CCI		

CCI Effective Date: 26 Nov 19

[figure not shown]
GALDERMA R&D	
RD.06.SPR.204245	

CD5789.SPR204245.SAP.V01 - Final Version 03F 1.0

Statistical Analysis Plan

CCI Effective Date: 26 Nov 19

CONFIDENTIALProject Document Version No. 1.0Project Document Effective Date: Date of last signature
Page 32 of 43

Approved

4.11 Safety Evaluation

Summaries based on observed cases (OC) will be provided for all safety measures. For these summaries, no data will be imputed. All safety summaries will be based upon the Safety population.

Line plots and bar charts over time based on observed cases (OC) will be provided for each local tolerability parameter. These plots and charts will be based upon the Safety population and no data will be imputed.

4.11.1 Extent of Exposure

The mean daily amount of topical drug applied will be calculated as the difference between the weight (in grams) of dispensed pumps and the weight (in grams) of returned pumps (missing pumps not returned by the subjects are assigned a weight difference of 45.0 grams for US sites and 75.0 grams for EU sites - the nominal fill weight of topical drug - for the aim of this calculation, supposing their content was completely used) divided by the number of days of use of the pumps (calculated as the difference between the date of compliance assessment and the dispensing date of each pump). The date of compliance assessment will be used instead of the actual pumps return date in order to avoid

CCI

GALDERMA R&D RD.06.SPR.204245

an overestimation of the number of days of use in case of delayed return of the pumps and to estimate the number of days of use in case of pumps not returned. Small differences (up to 0.5 g) between weights of dispensed and returned pumps are deemed due to weighting errors and thus are ignored and handled as no differences.

The mean daily amount of topical drug applied will be listed and summarized at each visit and overall by treatment group and overall in the Safety population.

Mean daily amount of topical drug applied by each subject will be presented in the by-subject listing of drug accountability.

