Other a :	This category is to be used for a subject who discontinues due to a reason other than as specified in the predefined categories above. Explain the reason for discontinuation in the comment section of the Exit Form.

<sup>a If reason for discontinuation is "withdrawal by subject", "withdrawal by parent/guardian", "physician decision" or "other", the subject will be questioned to rule out the possibility of an AE (this should be documented in the comment section of the Exit Form).

The reason(s) for withdrawal will be documented in the CRF. Subjects who have been randomized will not be replaced by another subject.

GALDERMA R&D RD.06.SPR.204245 V00 18AUG2021 Page 38 of 104

Subjects who prematurely discontinue study drug will be encouraged to complete the scheduled study visits for safety purposes and for collecting at least the data for the primary endpoint, before study exit.

When a subject discontinues the study, he/she will be fully assessed whenever possible, and followed according to guidelines presented in Section 5.5.1 - Early Termination Visit.

Reasonable efforts will be made to contact subjects who are lost to follow-up (e.g., non-response/contact after 2 phone calls and a certified letter with return receipt). These efforts must be documented in the subject's file.

The Sponsor has the right to terminate the study at any time in case of SAEs or if special circumstances concerning the investigational product or the company itself occur, making further treatment of subjects impossible. In this event, the investigator(s) will be informed of the reason for study termination.

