## a) Rechallenge with Assigned Topical Study Medication

- 1. After all signs and symptoms of AESI have resolved and after a minimum of two weeks from last topical dose application, perform a rechallenge test with the assigned topical study drug. Scheduling on a Monday or Tuesday is ideal, as it ensures the 48-hour and 72-96 hour follow-up assessments occur on weekdays (Table 10).
- 2. Ensure the subject has not been under any treatment with corticosteroids or antihistamines of any route of administration the Week before testing.
- 3. Ensure that the skin on the back has not been exposed to the sun or artificial ultraviolet sources the Week before testing.
- 4. Apply an appropriate quantity of the assigned topical study drug to fill in the cupule of the test chamber to a naïve zone on the back either the right or left side of the center line (or the inner forearm if the back cannot be tested). If no test chamber is available on site, patch test units will be provided by the Sponsor or designee. Apply an empty test chamber as a control for the rechallenge test with assigned topical study drug (note: an empty test chamber will not be needed for ingredient testing, if such test is warranted, as the Sponsor/designee will provide one or more controls for testing). The use of semi-occlusive conditions depends on the irritant potential of the study product and the intensity of the reaction that was observed. The method to be used should be discussed with the Medical Monitor.

Choose a skin site that was not previously involved in the inflammatory skin reaction. Cover the test chamber for 48 hours with a hypoallergenic tape.

- 5. Subject should be informed about avoiding exercise, showers, application of toiletries products, etc., to keep the test system dry
- 6. After 48 hours, remove the test chamber and evaluate the site and take photos after each reading (Table 10):

- at approximately 30 minutes after patch test removal (1st reading) and,
- 24 to 48 hours later (i.e., 72 or 96 hours after application) (2nd reading).
- If the result of the second reading is equivocal, the Investigator or at the Sponsors request, may perform an optional 3rd reading at 96 to 120 hours later (i.e., 6 to 7 days after application of the patch).
- Pictures of each reading and the reading results should be sent to Parexel Pharmacovigilance and medical monitor.

**Table 10:** Patch Testing Readout Schedule

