4.9 Treatment Compliance

4.9.1 Study Duration and Treatment Duration

For randomized and treated subjects, study duration will be calculated relative to the reference start date (i.e., first treatment date) as Study Duration = End of Participation Date – First Treatment Date + 1.

For randomized but not treated subjects, study duration will be calculated relative to the reference start date (i.e., date of randomization) as Study Duration = End of Participation Date - Randomization Date + 1.

For randomized and treated subjects, treatment duration will be calculated relative to the date of first treatment as Treatment Duration = Last Treatment Date - First Treatment Date + 1.

Study duration and treatment duration will be summarized for each treatment group and overall based upon the ITT population.

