4.9.2 Compliance and Drug Accountability

The compliance will be calculated for each visit and globally as:

Actual applications

Planned Applications – Missed Applications due to Prescribed Dose Reductions \times 100

CCL

For the overall compliance:

- Overall actual applications will be derived as the sum of actual applications at each visit. For treated subjects with no drug accountability information, overall actual applications will be calculated as Date of Last Treatment as collected in the End of Treatment form minus Date of First Treatment as collected in the End of Treatment form plus 1. If Date of Last Treatment is not collected in the End of Treatment form, overall actual applications will be set to 1.
- Overall planned applications will be derived as date of study completion/discontinuation minus date of baseline visit.
- Overall missed applications due to prescribed dose reductions will be derived as the sum of missed applications due to prescribed dose reductions at each visit.

Number and percentage of subjects compliant defined as having a compliance between 80% and 120% will be summarized by treatment group and overall.

Additionally, compliance expressed in percentage and by category (<80%; 80%-120%; >120%) will be summarized by visit and globally and will be presented for each treatment group and overall based upon the ITT population.

By-subject listings will be presented for compliance and drug accountability. .

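### Days of use in SAP 4.11.1 run to the compliance assessment, so the mean daily amount is understated for a subject who stops earlier and returns the pump

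*SAP*

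**What the plan says.** SAP 4.11.1 defines the mean daily amount as the weight difference between dispensed and returned pumps, divided by the days of use of the pumps. Those days are "calculated as the difference between the date of compliance assessment and the dispensing date of each pump". The reason given concerns late or missing pumps only: "The date of compliance assessment will be used instead of the actual pumps return date in order to avoid" too long a count when a pump comes back late, and to supply a count when it does not come back at all. In the numerator, "missing pumps not returned by the subjects are assigned a weight difference of 45.0 grams for US sites and 75.0 grams for EU sites", on the supposition that they were emptied.

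The result is descriptive: "The mean daily amount of topical drug applied will be listed and summarized at each visit and overall by treatment group", in the Safety population, with each subject's value in the accountability listing.

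Elsewhere the plan does hold the date on which the cream was stopped. SAP 4.9.2 refers to the "Date of Last Treatment as collected in the End of Treatment form", and SAP 4.9.1 uses it: "Treatment Duration = Last Treatment Date - First Treatment Date + 1". Protocol 5.3.4 expects visits to go on after a stop: "Subjects who prematurely discontinue study drug will be encouraged to complete the scheduled study visits".

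**The concern.** A clinic visit closes the count, and dispensing visits are four weeks apart (Protocol 5.4.6.3). A subject can therefore stop the cream early in an interval, attend the next visit with the pump, and have every day since the last application counted as a day of use. The SAP sets out to avoid overcounting these days but guards only against late pump return.

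In the readable text this is the only measure of grams applied. The subjects concerned include those who stop for irritation: cutaneous events leading to permanent discontinuation are adverse events of special interest (Protocol 6.3.6.1.3). A reader who sets these events beside the daily amount could take an early stopper who applied a normal or large amount for someone who applied very little.

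**Working it through.** SAP 4.11.1 states no computed exposure figure, so there is none to reproduce.

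**Inputs**
- Pump interval: 28 days (Protocol 5.4.6.3, dispensing at Baseline and Weeks 4, 8, 12, 16 and 20).
- Fill assigned to unreturned pumps: 45.0 g (US), 75.0 g (EU) (SAP 4.11.1).
- True daily use on the face: not in the documents; assumed 0.25 to 1.5 g/day. The nearest figure is 1.5 to 2 g/day in the label's pharmacokinetic study, which covered the face, shoulders, chest and upper back (Protocol Appendix 14.9, section 12.3).
- Stop rates by group and pump non-return rates: not in the documents; varied below.

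**1. Returned pump.** The grams are the same under either denominator, so SAP value / amount per day on drug = days on drug / days counted.
- Stop after 7 days: 7/28 = 0.25
- After 14 days: 14/28 = 0.50
- After 21 days: 21/28 = 0.75

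These ratios do not depend on grams per application.

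**2. A worked case.** Pump dispensed Day 29, last application Day 33, assessment Day 57, pump returned. Days counted: 57 − 29 = 28. Days on drug: 33 − 29 + 1 = 5. The interval value is 28/5 = 5.6 times too low. Over the whole period, taking total grams over total days and even use, 28 + 28 = 56 days are counted against 28 + 5 = 33 on drug: 33/56 = 0.589, or 41% too low. Later stops are diluted by earlier intervals. With 14 off-drug days, the overall ratio is 14/28 = 0.50, 70/84 = 0.83 or 154/168 = 0.92.

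**3. Unreturned pump.** The SAP value is 45/28 = 1.61 g/day (US) or 75/28 = 2.68 g/day (EU), whatever the stop day. Relative to assumed true use:

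| True g/day | US | EU |
|---|---|---|
| 0.25 | 6.4 | 10.7 |
| 0.5 | 3.2 | 5.4 |
| 1.0 | 1.6 | 2.7 |
| 1.5 | 1.07 | 1.79 |

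These are overstatements throughout the assumed range.

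**4. Group mean, first interval.** Let a share f stop after 14 of 28 days, a share q of those not return the pump, and true use be g. For US pumps:

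ratio = (1 − f) + f × [(1 − q) × 0.5 + q × (45/28)/g]

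With g = 0.5:
- q = 0: 0.975, 0.95 and 0.85 for f = 5%, 10% and 30%.
- q = 25%: 1.009, 1.018 and 1.054 for the same f.

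The sign changes at q = 0.5g / (45/28 − 0.5g) = 0.25/(1.607 − 0.25) = 18% (US). With 75/28 in place of 45/28 it is 0.25/(2.679 − 0.25) = 10% (EU). At g = 1.0 the thresholds are 45% and 23%.

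**5. Capping an unreturned pump.** If the pump in step 2 were not returned, ending its days at the last application would give 45/5 = 9 g/day or 75/5 = 15 g/day, in place of 1.61 or 2.68.

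**6. Interruption followed by resumption.** The last treatment date is unchanged, so a cap there does nothing. Fourteen days on alternate days leave 21/28 = 0.75 in that interval and 161/168 = 0.96 over 24 weeks, with or without the cap.

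**The case against.** The strongest reply is that grams per calendar day is a legitimate average, and that an early stopper can be recognised from other outputs: treatment duration (SAP 4.9.1), compliance by visit and overall (4.9.2), dose reductions (4.9.3) and the by-subject accountability listing. This largely stands against any claim that over-application would be hidden. It does not rescue the definition, because the SAP calls its denominator days of use and chooses the date so as not to overcount them.

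A second reply also stands. Subjects who leave the study should have the early termination procedures (Protocol 5.5.1), which include product return and compliance review. If that visit follows soon after the last application, there is almost nothing to correct. Compliance is also checked at Weeks 1 and 2, although the SAP does not say which check closes the Baseline pump.

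Three stronger readings are tempting but unsupported:
- That everyone who stopped is understated, and the group with more stops looks under-dosed. The full-fill rule pushes the other way. The label shows more irritation on active cream than on vehicle (application site irritation 7.5% against 0.3%), but the documents give no stop rates by group. The 30% in the sample size section is total drop-out, not subjects who stop the cream and attend weeks later.
- That a suspected contact reaction adds at least 14 + 3 = 17 days, because rechallenge comes "after a minimum of two weeks from last topical dose application" and the second reading is at 72 hours or later. Days are counted per pump and scheduled visits continue meanwhile (Protocol 6.3.6.2.4), so a reaction just before a visit adds only a few days.
- That SAP 4.9.1 and 4.11.1 contradict each other. They define different quantities and may differ.

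**Conclusion.** The point holds for a subject who stops before the compliance assessment and returns the pump: the mean daily amount is understated in that interval in proportion to the off-drug days counted. The size ranges from negligible, when the assessment follows closely, to several-fold for a stop soon after dispensing. This assumes no further pump is dispensed after the stop, which confines the error to the last interval; the overall figures also assume pooling of grams and days.

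No direction can be given for either treatment group, since that depends on stop rates, pump non-return and true use, none of which the documents supply. The consequence is limited to a descriptive summary and listing. The primary analysis, compliance, treatment duration, analysis sets and sample size are unaffected. It is a minor correction, but worth making because the rule falls short of its own stated aim and the date needed is already collected.

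**What to change.** In SAP 4.11.1:
- For returned pumps, end days of use at the earlier of the compliance assessment date and the recorded last treatment date, counting the last treatment day. Keep the present rule when the last treatment date is missing.
- For unreturned pumps, do not apply this cap. Summarise the mean daily amount with and without the full-fill assumption.
- Optionally, list grams per recorded application (weight used divided by actual applications). This also covers interruptions followed by resumption, without needing interruption dates, which the visible text does not show as a collected field.

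The cost is a few lines of SAP text, a little more programming and one extra summary. The cap needs no new data.
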